7.5.1. Adverse Events

7.5.1.1. Definitions

Adverse Event

According to the International Council for Harmonisation (ICH) E2A guideline Definitions and Standards for Expedited Reporting, and 21 CFR 312.32, investigational new drug (IND) Safety Reporting, an AE is any untoward medical occurrence in a patient or clinical investigational subject administered a medicinal product and which does not necessarily have a causal relationship with this treatment.

The following information should be considered when determining whether or not to record a test result, medical condition, or other incident on the Adverse Events and Pre-existing Conditions CRF:

- All study protocol-related AEs that occur after the consent form is signed but before treatment allocation must be reported by the investigator.
- All medical conditions present or ongoing predose on study Day 1 should be recorded.
- All AEs (regardless of relationship to study drug) should be recorded from study Day 1
 through the end of the safety reporting period (see Section 6). Complications that occur in
 association with any procedure (e.g., biopsy) should be recorded as AEs whether or not
 the procedure was protocol mandated.

- Changes in medical conditions and AEs, including changes in severity, frequency, or character, during the safety reporting period should be recorded.
- In general, an abnormal laboratory value should not be recorded as an AE unless it is
 associated with clinical signs or symptoms, requires an intervention, results in a SAE, or
 results in study termination or interruption/discontinuation of study treatment. When
 recording an AE resulting from a laboratory abnormality, the resulting medical condition
 rather than the abnormality itself should be recorded (e.g., record "anemia" rather than
 "low hemoglobin").

Serious Adverse Events

An AE should be classified as an SAE if it meets one of the following criteria:

Fatal:	AE resulted in death
Life threatening:	The AEs placed the patient at immediate risk of death. This classification does not apply to an AE that hypothetically might cause death if it were more severe.

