# Appendix A Imputation of Partially Unknown Adverse Event Dates

For a pre-existing condition and adverse event (AE) with a partial start or end date, if it can be determined that the event occurred prior to the date of first dose of study treatment, the partial date will not be imputed; Otherwise, the partial date will be imputed using the rules described below. For ease of reading, both pre-existing conditions and AEs will be referred to as AE for the remainder of this document. AE start dates should be imputed before imputation of AE condition end date in all cases.

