# AE day, month and year are missing, or year only is missing

AE condition end date will not be imputed

Within a single record, if the imputed stop date is before the start date, then the imputed stop date will be equal to the start date.

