# Appendix C Definition of the Term "Treatment-Emergent" with Respect to AE Classification

The algorithm below should be used to determine whether an adverse event (AE) is classified as a treatment-emergent adverse event (TEAE). A TEAE is defined as any AE which worsens in severity during the safety reporting period or is newly occurring at any time, where newly occurring means that the AE was not present at baseline. For ease of reading, both pre-existing conditions and AEs will be referred to as AEs for the remainder of this document. AE dates should be imputed in accordance with the algorithm detailed in Appendix A prior to determination of TEAE classification. Details of the TEAE classification are as follows:

- For each patient, determine the first dose date, which is the earliest date the patient receives any amount of study drug.
- Baseline AEs: classify an AE record as baseline AE if it satisfies both criteria a and b below:

AE onset satisfies either of i, ii or iii below:

- Onset date is prior to the first dose date
- ii. Onset date is the same as the first dose date, and Onset Period is "started after consent but before the first dose of any study treatment" or Onset Time Relative to Study Treatment is "started before first infusion or before infusion on any dosing day"
- iii. Onset Period is "started before the signing of consent" or "started after consent but before the first dose of any study treatment"

AE end date satisfies either of i or ii below:

- End date is the same as or after the first dose date
- End date is missing with outcome equal to

recovering/resolving, or

not recovered/not resolved, or

unknown or missing

- Post-baseline AEs: classify an AE record as post-baseline AE if it meets either of criteria a, b or c below:
  - a Onset date is after the first dose date
  - b Onset date is the same as the first dose date, and Onset Period is "started after the first dose of any study treatment" or Onset Time Relative to Study Treatment is not "started before first infusion or before infusion on any dosing day"
  - c Onset Period is "started after the first dose of any study treatment"
- TEAE flag will be derived as follows:
  - For all AE records that have an end date prior to the first dose date, assign TEAE flag to 'N'
  - For all baseline AEs, assign TEAE flag to 'N'
  - c. For post-baseline AEs:
    - If the post-baseline AE is a continuing event of a baseline AE (i.e., events with

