      the same AE identifier, where AE identifier is the number before the colon in
      SDTM AE.AESPID), then compare the post-baseline AE to the most recent
      baseline AE with the same AE identifier (to be referred to as "baseline AE"
      below). Assign TEAE flag to "Y" for the applicable post-baseline AE records, if a

Study SGNLVA-002 Ladiratuzumab vedotin Statistical Analysis Plan Seagen, Inc. - Confidential 01-May-2024 Page 27 of 32 post-baseline AE record meets any of the following worsening criteria based on relatedness, seriousness or CTCAE grade:

- If the post-baseline AE is related to treatment, or
- If the post-baseline AE meets the criteria for an SAE and the most recent baseline AE was not an SAE, or
- If the post-baseline AE has a higher CTCAE grade

All subsequent episodes of the same AE should have TEAE flag = 'Y'.

- Otherwise, assign TEAE flag to 'N'
- If the post-baseline AE is not a continuing event of a baseline AE, then assign TEAE flag to 'Y

NOTE: For summaries which include only treatment emergent AEs, include all AEs which have at least one record classified as aTEAE as well as those AEs for which TEAE status could not be determined (e.g., the value of the TEAE variable may be missing if the event cannot be identified as baseline or post-baseline – missing information on the AE CRF should be queried). Only exclude those AEs which were determined to not be treatment emergent for all records.

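### SAP Appendix C gives no TEAE flag to a pre-dose-onset record with a resolved outcome and a missing end date, and its NOTE then counts that record as treatment-emergent

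*SAP*

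**What the plan says.** Protocol 7.5.1.1 puts pre-existing conditions on the same CRF as adverse events: "All medical conditions present or ongoing predose on study Day 1 should be recorded". SAP Appendix C processes the two together.

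For baseline status Appendix C says "classify an AE record as baseline AE if it satisfies both criteria a and b below". Criterion a concerns onset, for example "Onset date is prior to the first dose date", or an Onset Period before the first dose. Criterion b concerns the end: either "End date is the same as or after the first dose date", or "End date is missing with outcome equal to" recovering/resolving, not recovered/not resolved, or unknown/missing. Recovered/resolved and recovered/resolved with sequelae are not on that list, although Appendix A names both as outcomes.

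The flag rules then assign N if the end date precedes first dose (rule a) and N to every baseline AE (rule b). Post-baseline AEs are assessed under rule c. The NOTE brings in AEs with at least one treatment-emergent record "as well as those AEs for which TEAE status could not be determined". It excludes an AE only when all its records were determined not to be treatment-emergent, and it asks for missing CRF information to be queried.

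Appendix A imputes some partial end dates. When the year, or the whole end date, is missing, "AE condition end date will not be imputed".

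**The concern.** SAP 6.7.1 defines a TEAE as an event that is new or has worsened after first dose. A record whose onset is placed before first dose is not new after first dose, and a record that merely lacks an end date shows no worsening. For one combination of outcome and missing date, the rules nevertheless leave the status open, and the NOTE resolves it toward inclusion.

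The incidence of AEs is a primary safety endpoint (SAP section 2), and the TEAE tables by preferred term are its main display. The study has a single arm, so no control group would carry the same miscount and offset it.

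**Working it through.** The plan states no figure on this point to reproduce, so the check follows the rules.

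**1. One record through Appendix C.** Take onset before first dose, outcome recovered/resolved, end date missing.

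| Test | Needs | Result |
|---|---|---|
| Baseline a | pre-dose onset by date or Onset Period | met |
| Baseline b-i | end date on or after first dose | not met, no date |
| Baseline b-ii | missing end date with a listed outcome | not met, outcome not listed |
| Post-baseline a, b, c | onset after first dose, or same day and not pre-dose, or post-dose Onset Period | not met |
| Flag rule a | end date before first dose | cannot be applied |
| Flag rules b, c | baseline or post-baseline status | do not apply |

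The flag is empty, so the NOTE includes the AE.

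**2. What the missing date could have been.**

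- End before first dose: rule a gives N.
- End on or after first dose: baseline b-i is met and rule b gives N.

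No third case exists. Every possible end date gives N, while the absence of the date leads to inclusion.

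**3. All combinations.** Five onset types (before dose; same day but pre-dose; date missing with a pre-dose Onset Period; same day post-dose; after dose), three end-date states (before dose; on or after dose; missing) and seven outcomes give 5 × 3 × 7 = 105. For three of the onset types an end before first dose would precede onset, which removes 3 × 7 = 21 and leaves 84.

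- Undetermined: 9 of 84, all with pre-dose onset and a missing end date (3 onset types × 3 outcomes: recovered, recovered with sequelae, fatal).
- With the two resolved outcomes that concern us here: 3 × 2 = 6.
- With post-dose onset: none undetermined.

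The same-day rows assume that Onset Period and Onset Time Relative to Study Treatment agree.

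**4. Which records reach step 1 after Appendix A.** For a resolved outcome:

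- *Day missing.* The end date becomes the earliest of death date, extraction date, last day of that month and EOS date. If the recorded month is that of first dose or later, each of these is on or after first dose, so the record is baseline and N.
- *Month missing, or day and month missing.* The same argument holds with 31 December of that year and, if the year is that of last dose, last dose + 30 days. The result is N if the year is that of first dose or later.
- *Partial date clearly before first dose.* Not imputed, but it can be read as N under rule a.
- *Year missing, or whole date missing.* Not imputed, so the gap applies.

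One sentence in Appendix A leaves doubt: where it can be determined that "the event occurred prior to the date of first dose of study treatment, the partial date will not be imputed". If this refers to onset alone, partial end dates of pre-dose-onset records would also stay open. The worked nausea example speaks against applying it to a whole event: the AE began before consent, yet the partial end date on its second line is imputed to 30 April 2012. That line itself starts after first dose, so the example does not settle the reading for a single record.

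**5. Weight of one record.** A patient counts once per preferred term. In Part D, with about 40 patients, one wrongly included patient moves one term by 1/40 = 2.5 percentage points. Among the 62 patients planned at 1.25 mg/kg in Part C it is 1/62 = 1.6 points. Both apply only if the patient has no genuine TEAE under the same term.

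**The case against.** The strongest reply is that the authors foresaw empty flags. The NOTE orders missing information to be queried, and Protocol 7.5.1.2 requires resolution dates to be recorded, so a resolved event without one is an obvious query. Inclusion is then a cautious default for what remains. Appendix A removes most of the inflow, because the year in which a condition resolved under follow-up is usually known. The study is descriptive with no formal testing (SAP 5.7), residual error leans toward over-reporting, and all AEs are listed, so a misplaced record stays visible.

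Most of this stands, and it limits the size. It does not rescue the rule. Default inclusion is sensible when onset cannot be placed; here onset is placed, and step 2 shows that the missing date cannot change the answer.

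Two stronger readings are tempting:

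- *That the plan works backwards, counting pre-existing conditions that resolve and excluding those that persist.* The documents do not support this as a general statement. A resolution dated before first dose is N by rule a, and one dated on or after first dose is N by rule b. Only resolved records without a usable end date fall through.
- *That TEAE incidence is materially inflated.* The documents give neither the number of pre-existing conditions per patient nor the share without an end date, and any rate that counts all incomplete dates would include those Appendix A imputes.

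**Conclusion.** Appendix C is wrong as written for one narrow combination: onset placed before first dose, outcome recovered/resolved or recovered/resolved with sequelae, and an end date still missing after Appendix A imputation and after querying. In practice that means the year is missing. Such a record enters the TEAE summaries although every possible end date would make it N.

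The number of records cannot be stated from the documents and is probably small. The direction is known: TEAEs are over-counted, never under-counted. This rests on reading Appendix A as imputing end dates with a known year for resolved outcomes; if its opening sentence means onset alone, more records are affected. The point is a small correction to a derivation rule and does not call the safety analysis as a whole into question.

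**What to change.** In SAP Appendix C:

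1. Add a flag rule: a record whose onset is placed before first dose, by date or Onset Period, with outcome recovered/resolved or recovered/resolved with sequelae and a missing end date, is assigned N for that record only.
2. State that such a record does not become the baseline comparator for later records with the same AE identifier. The condition may have ended before first dose. If it served as comparator, a later same-grade, unrelated, non-serious recurrence would turn from Y to N under rule c, and a genuine TEAE could be lost. Under the current text that recurrence is Y, and it should stay so.
3. Limit the NOTE's default inclusion to AEs whose onset cannot be placed relative to first dose, and keep the query instruction.

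This settles 6 of the 9 undetermined combinations and changes none with post-dose onset. The other 3 are pre-dose onset with a fatal outcome and no end date; they should be closed by query against the death date before lock. It would also help to say in Appendix A whether the exemption for pre-dose events refers to onset or to the date being imputed.

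The cost is a few lines of SAP text and one condition in the derivation program. No data collection changes.

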# APPENDIX D RECIST CRITERIA SUMMARY (VERSION 1.1)

Response Evaluation Criteria for Solid Tumors		
Term	Definition	
Complete response (CR)	Disappearance of all target lesions. Any pathological lymph nodes must have reduction in short axis to <10 mm.	
Partial response (PR)	$A \ge 30\%$ decrease in the sum of diameters of target lesions, taking as reference the baseline sum diameters.	
Progressive disease (PD)	At least a 20% increase in the sum of diameters of target lesions, taking as reference the smallest sum on study (this includes the baseline sum if that is the smallest on study). In addition to the relative increase of 20%, the sum must also demonstrate an absolute increase of at least 0.5 cm. The appearance of one or more new lesions is also considered progression.	
Stable disease (SD)	Neither sufficient shrinkage to qualify for PR nor sufficient increase to qualify for PD, taking as reference the smallest sum diameters while on study.	
Measurable lesion	Must be accurately measured in at least one dimension (longest diameter in the plane of measurement is to be recorded) with a minimum size of 10 mm by CT scan (CT slice thickness no greater than 5 mm).	

From RECIST Version 1.1 (Eisenhauer 2009)

Best overall response when confirmation of CR and PR required				
Overall response First time point	Overall response Subsequent time point	Best overall response		
CR	CR	CR		
CR	PR	SD, PD or PR a		
CR	$SD_p$	SD provided minimum criteria for SD duration met, otherwise, PD		
CR	PD	SD provided minimum criteria for SD duration met, otherwise, PD		
CR	NE	SD provided minimum criteria for SD duration met, otherwise, NE		
PR	CR	PR		
PR	PR	PR		

Study SGNLVA-002 Ladiratuzumab vedotin Statistical Analysis Plan Seagen, Inc. - Confidential 01-May-2024 Page 29 of 32

PR	$SD_p$	SD
PR	PD	SD provided minimum criteria for SD duration met, otherwise, PD
PR	NE	SD provided minimum criteria for SD duration met, otherwise, NE
NE	NE	NE

CR = complete response, PR = partial response, SD = stable disease, PD = progressive disease, and NE = inevaluable.

a If a CR is truly met at first time point, then any disease seen at a subsequent time point, even disease meeting PR criteria relative to baseline, makes the disease PD at that point (since disease must have reappeared after CR). Best response would depend on whether minimum duration for SD was met. However, sometimes 'CR' may be claimed when subsequent scans suggest small lesions were likely still present and in fact the patient had PR, not CR at the first time point. Under these circumstances, the original CR should be changed to PR and the best response is PR.

b In cases where the initial response is followed by SD, it will be considered as confirmed if the SD is later followed by PR or CR. For example, if a patient had PR in first time point, SD in subsequent time point, and PR in the following time point, this PR will be considered as confirmed.

Modified from RECIST Version 1.1 (Eisenhauer 2009)

# Appendix E RECIST Response Confirmation Algorithm Details

A response (CR or PR) will be considered confirmed (RSCONFL=Y) if the following disease assessment (at least 4 weeks after the initial response) still shows response (CR or PR).

#### Note:

Only timepoint responses prior to new anti-cancer therapy are considered.

To classify response throughout the study, if start day of new anti-cancer therapy exists, then set B= start day of new anti-cancer therapy, otherwise B=999999.

Set A=35 days (protocol-specified minimal days for assessment of SD, the earliest day in the

Set A=35 days (protocol-specified minimal days for assessment of SD, the earliest day in the window of first scheduled assessment.).

Days A and B define the time windows for the records to be included in the best overall response assessment.

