#### 5.4.3 Best Response

Primary analysis of response will be based on RECIST Version 1.1.

A patient's best response will be the best demonstrated response to date that has been confirmed. Confirmation is required for PR and CR only. Once a patient achieves a confirmed PR, only evidence of CR will potentially change the patient's confirmed best response. The patient's best response will be used in determining the ORR.

Study SGNLVA-002 Ladiratuzumab vedotin Statistical Analysis Plan Seagen, Inc. - Confidential 01-May-2024 Page 13 of 32 Per RECIST Version 1.1, a response (CR or PR) will be considered confirmed if the following disease assessment (at least 4 weeks after the initial response) still shows response (CR or PR). A patient will have a best response of SD if there is at least one SD assessment (or better) >5 weeks after the start of treatment and the patient does not qualify for CR or PR. The details of best response are provided in 0 and Appendix E.

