# 6.6.1 Efficacy Endpoints

# 6.6.1.1 Objective Response Rate (ORR)

ORR is defined as the proportion of patients with confirmed CR or PR according to RECIST Version 1.1. Patients who do not have at least 2 (initial response and confirmation scan) postbaseline response assessments will be counted as non-responders.

The observed ORR and the 95% confidence intervals will be provided using Clopper-Pearson methodology.

The maximum percent reduction (or minimum percent increase if there is no reduction) in the sums of diameters from baseline will be derived for each patient and will be graphically displayed (e.g., using a waterfall plot).

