#### 6.6.1.3 Disease Control Rate

Disease control rate (DCR) is defined as the proportion of patients with CR, PR, or SD per RECIST Version 1.1.

The observed DCR and the 95% confidence intervals will be provided for the All Treated analysis setusing Clopper-Pearson methodology, by expansion cohorts and overall.

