# 6.6.1.4 Progression-Free Survival (PFS)

Progression-free survival (PFS) is defined as the time from start of study treatment to first documentation of disease progression (PD) based upon the disease assessment per RECIST Version 1.1 or clinical progression, or to death due to any cause, whichever comes first. For patients who are enrolled but fail to receive study treatment, the enrollment date will be used as the starting point in the calculation in PFS. Specifically,

PFS = Date of first documented PD or death - Date of first study treatment +1

The same censoring rules outlined for DOR will be applied to PFS. Patients lacking an evaluation of tumor response at baseline and/or after their first dose will have their event time censored at Day 1.

PFS will be analyzed using the Kaplan-Meier method and Kaplan-Meier plots will be provided. The median PFS and its two-sided 95% confidence intervals (CI) will be calculated using the complementary log-log transformation method (Collett 1994) by expansion cohorts and overall.

Page 18

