# Best Overall Response Algorithm:

Set best overall response to CR if:

 Any record on or before study Day B has AVALC=CR and RSCONFL=Y, where AVALC is the response variable and RSCONFL is a derived variable as a flag for a confirmed responses. The algorithm of the confirmation flag is outlined below in section "Derivation Algorithm for Confirmation Flag (RSCONFL)".

Otherwise set to PR if:

Any record on or before study Day B has AVALC=PR and RSCONFL=Y.

Otherwise set to SD if:

- Any record between study Day A and B, inclusive, has AVALC=SD; or
- Any record between study Day A and B, inclusive, has AVALC=CR/PR and RSCONFL=N.

Otherwise set to PD if:

Any record on or before study Day B has AVALC=PD.

Otherwise set to NE.

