#### Derivation Algorithm for Confirmation Flag (RSCONFL)

- For records with AVALC=CR or PR,
  - a) Set to Y if CR/PR is confirmed,
  - Set to N if the next available scan did not confirm the response (e.g. PR followed by PD).
  - Set to missing if there is no available scan to confirm the response (eg. at interim data cut)

Study SGNLVA-002 Ladiratuzumab vedotin Statistical Analysis Plan Seagen, Inc. - Confidential 01-May-2024 Page 31 of 32

- For all other records (eg. AVALC not CR or PR), leave the value for the variable RSCONFL as missing.
- Confirmation means a PR is followed by a PR or CR (ignoring two NEs or 1SD in between) at least 28 days (4 weeks) later (ie, date of second PR/CR − date of first PR ≥28), or a CR is followed by a second CR (ignoring two NEs in between) at least 28 days later. If there are 2 NEs between 2 responses, the 2 responses need to be within 3 months.
- CR followed by PR should be considered as data issue, and will not be considered a confirmed PR at the time of the previous (initial) CR.

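### The SAP's best-response rule does not stop at first RECIST v1.1 progression, so a PR that begins after PD and is later confirmed counts in the primary ORR although PFS has already ended

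*SAP*

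**What the plan says.** SAP 6.6.1.1 defines the primary endpoint: "ORR is defined as the proportion of patients with confirmed CR or PR according to RECIST Version 1.1". SAP 5.4.3 says the patient's "best response will be the best demonstrated response to date that has been confirmed" and feeds that into ORR.

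Appendix E turns this into code. Its Note bounds the records by Day B: "if start day of new anti-cancer therapy exists, then set B= start day of new anti-cancer therapy, otherwise B=999999". The algorithm then works in order: confirmed CR; confirmed PR, if "Any record on or before study Day B has AVALC=PR and RSCONFL=Y"; SD, if "Any record between study Day A and B, inclusive, has AVALC=SD" or if a CR/PR in that window is flagged as not confirmed; PD; otherwise NE. The flag `RSCONFL` looks only forward from the response: "a PR is followed by a PR or CR (ignoring two NEs or 1SD in between) at least 28 days" later.

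Two secondary endpoints depend on the same records or dates. DCR "is defined as the proportion of patients with CR, PR, or SD per RECIST Version 1.1" (SAP 6.6.1.3). PFS stops at the first progression: "PFS = Date of first documented PD or death - Date of first study treatment +1" (SAP 6.6.1.4). DOR runs from first response to first documented progression, radiologic or clinical, or death (SAP 6.6.1.2).

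**The concern.** First PD is not a bound anywhere in the best-response rule. The PD step is reached only after the CR, PR and SD steps have failed, so a progression is overridden by anything better that follows it before new therapy. The other summaries do not supply the missing stop. SAP Appendix D measures PR against the baseline sum, has no best-response row that starts with PD, and (footnote a) converts a later PR to PD only after a true CR. Protocol 9.2.1 and Appendix J add no cut.

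The protocol allows the pattern to arise. Treatment continuation is judged by iRECIST (Protocol 3.1 and 7.2), and Protocol Appendix K places a confirmatory scan 4 to 8 weeks after an unconfirmed progression. If that scan shows shrinkage, progression is not confirmed and imaging can continue.

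At stake is the consistency of the endpoints: one patient can be a PFS event and later a responder. Protocol 3.2 added iRECIST because standard RECIST may misjudge late immune responses. SAP 8.2 drops the iRECIST endpoints, and Appendix E can then let those same responses into the RECIST v1.1 rate without labelling them.

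**Working it through.** **The plan's own figures.** Clopper-Pearson limits reproduce all six tabulated intervals in SAP 5.2.3 and 5.2.4. For example, 31/62 gives 37.0–63.0% (stated 37–63) and 20/40 gives 33.8–66.2% (stated 34–66).

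**Can the pattern occur?** Scans every 6 weeks fall on Study Days 43, 85, 127 and 169. For PD on Day 43, the Appendix K window is 43+28 = 71 to 43+56 = 99, and the scheduled Day 85 scan lies inside it. Take target sums of 100 mm at baseline, then 125, 65 and 65:
- 125/100 is +25% and +25 mm, which is PD.
- 65/100 is −35% from baseline, which is PR, twice.

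**Appendix E as code** (A = 35, no new therapy), as written and with the proposed corrections (cut at first PD before `RSCONFL`, plus the lone-PR change described under the fix):

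| Sequence | As written | Corrected |
|---|---|---|
| PD-PR-PR | PR | PD |
| SD-PD-PR-PR | PR | SD |
| PR-PD-PR-PR | PR | SD |
| PD-PR-SD | SD | PD |
| PD-PR-PD | SD | PD |
| PD-SD | SD | PD |
| PD-PR (last scan) | PD | PD |
| PR-PR-PD | PR | PR |
| PR-SD-PR | PR | PR |
| PR only | NE | SD |

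The first three rows change ORR. The next three change DCR only. Responders whose confirmation precedes PD are untouched. The earliest confirmed case inside the Appendix K window (PD Day 43, PR Day 71, PR Day 99, gap 28 days) also scores PR as written. If new therapy starts on Day 100, PD(43)-PR(85)-PR(127) scores PD, because Day B then applies.

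The last row is a separate, smaller gap. A lone PR has `RSCONFL` missing rather than N, so Appendix E gives NE, whereas SAP 5.4.3 gives SD for an assessment of SD or better more than 5 weeks after start. It affects DCR only.

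**Clash with PFS and DOR** for PD(43)-PR(85)-PR(127):
- PFS = 43 − 1 + 1 = 43 days.
- DOR = 43 − 85 + 1 = −41 days if the Day 43 PD is the end date. On any other reading, the end date is undefined.

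**Size.** One patient adds 100/N points. The number of post-PD responders is not in the documents, so 0 to 3 is an assumed range, on an assumed base of 50%:

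| N (source) | 0 | 1 | 2 | 3 | Exact 95% CI, 0 then 1 patient |
|---|---|---|---|---|---|
| 40 (Part D) | 50.0 | 52.5 | 55.0 | 57.5 | 33.8–66.2; 36.1–68.5 |
| 62 (Part C, 1.25 mg/kg) | 50.0 | 51.6 | 53.2 | 54.8 | 37.0–63.0; 38.6–64.5 |
| 60 (Parts A and B, MAD) | 50.0 | 51.7 | 53.3 | 55.0 | 36.8–63.2; 38.4–64.8 |
| 30 (Parts A and B, 2.0 mg/kg) | 50.0 | 53.3 | 56.7 | 60.0 | 31.3–68.7; 34.3–71.7 |

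**The case against.** The strongest reply is that these responses may never reach the RECIST v1.1 dataset. Protocol Appendix K gives iRECIST responses a prefix and records them separately, so the scan after an unconfirmed progression would be iPR, while Appendix E reads an unprefixed PR and the SAP's analysis is RECIST v1.1 only. This stands as a limit on the effect: if sites carry PD forward, nothing changes. It does not close the gap. The documents do not say how a RECIST v1.1 time point is coded after PD, and a programmer following Appendix E would count an unprefixed PR.

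Exposure is also narrow. Protocol 6.4 schedules imaging until progression, 6.6 ends response assessments after it, and 7.2 lets only clinically stable patients continue, at the physician's discretion. The patient then needs a fall of at least 30% below baseline, a second response at least 28 days later, and no new therapy before both scans. If PD came from a new lesion, shrinking target lesions would not obviously give an overall PR. These points make the case uncommon, not impossible.

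The trial is descriptive, with no hypothesis test (SAP 5.7), and one patient moves ORR by 1.6 to 3.3 points against exact intervals about 26 to 37 points wide. That is fair and argues against a higher severity. Finally, DOR can be read as looking forward from response; the −41 days arises only if the first-ever PD is its end date. That too is accepted, but on the forward reading the end date still needs defining.

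**Conclusion.** The concern holds and should be fixed. As written, the rule for the primary endpoint can score a patient as a responder after that patient's PFS event. The bias in ORR runs only upward. DCR is also raised by an SD after PD, or by a post-PD PR that the next scan does not confirm. The size is 1.6 to 3.3 points of ORR per patient across the planned group sizes, with the number of patients unknown and possibly zero. The conclusion about the text is firm. Any effect on the estimate depends on sites entering an unprefixed RECIST v1.1 PR after PD, and on both scans preceding new therapy. The lone-PR gap can lower DCR and cannot affect ORR.

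**What to change.** - In Appendix E, before deriving `RSCONFL` and best overall response, keep only time points up to and including the first RECIST v1.1 PD and before new anti-cancer therapy. Then neither a response nor its confirming scan can follow PD, and the PD record itself still reaches the PD step.
- Put the same sentence in SAP 5.4.3, and list post-PD responses separately.
- If investigator-claimed clinical progression is also adopted as a cut-off, to match PFS and DOR, apply it before `RSCONFL` and count it as PD in the PD step. Otherwise such patients could fall to NE.
- Separately, change the second SD condition to any CR/PR in the window whose `RSCONFL` is not Y, so that a lone PR on or after Day A is SD, as 5.4.3 states.

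The cost is a few lines of SAP text and code, with no new data. ORR can only stay the same or fall. DCR may fall from the cut-off or rise slightly from the lone-PR change.
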